STUDY PROTOCOL AND STATISTICAL ANALYSIS PLAN

OFFICIAL TITLE: Effects of a Single Maximal Exercise Session on the Metabolic Function of Physically Inactive Young Adults

BRIEF TITLE: Single Maximal Exercise Session and the Metabolic Response of Physically Inactive Young Adults (EASY-Study)

NCT number: unavailable

November 4th, 2024

STUDY PROTOCOL

TITLE: Effects of a Single Maximal Exercise Session on the Metabolic Function of Physically Inactive Young Adults (EASY-Study)

ABSTRACT

Background: Physical exercise has been proposed as an effective intervention for the normalization of metabolic alterations caused by long-term physical inactivity. In this sense, one of the potential mediators of this response is Fibroblast Growth Factor (FGF) 21, due to its actions as an insulin sensitizer in various target tissues (e.g. skeletal muscle and white adipose tissue), promoter of lipid oxidation and anti-inflammatory. Recently, it has been described that a potential mediator of FGF21 production is lactate, since, *in vitro* studies have shown that treatment with increasing concentrations of lactate, both in adipocytes and muscle cells, promotes greater production of FGF21. These findings suggest that this metabolite would play a relevant role in the regulation of circulating concentrations of FGF21. However, the evidence in this regard is based mainly on findings in cell cultures, highlighting the absence of clinical studies focused on solving this problem.

Aim: To investigate the influence of exercise-induced changes in blood lactate on plasma FGF21 concentration in physically inactive subjects.

Methodology: This is a quasi-experimental study with pre- and post-intervention measurements. 20 adults (10 women and 10 men), aged between 18 and 30 years, physically inactive (performing less than 150 minutes/week of moderate physical activity and/or 75 minutes/week of vigorous physical activity) and without medical contraindications to physical activity will be included. Additionally, those individuals who are on medications that influence blood glucose or insulin levels and/or with anti-inflammatory effects will be excluded.

To induce elevations in blood lactate, an incremental load test will be applied on a stationary bicycle, in which the pedaling load will be increased every 3 minutes (30W; maintaining a pedaling speed of 60-70 revolutions per minute) until reaching the point of fatigue. Before starting the test, resting variables such as heart rate, subjective sensation of effort (SSE), blood pressure, pulse oximetry and muscle (vastus lateralis of quadriceps) will be recorded. In addition, a venous blood sample will be taken in a 2 ml tube with EDTA and another tube without anticoagulant for the subsequent plasma measurement of FGF21 and complementary biochemical tests (glycemia, insulin, lipid profile, transaminases and renal function markers), in addition to the measurement of lactate from a finger prick with a sterile lancet. In addition, urine samples will be taken both before and after exercise to measure renal function markers (proteinuria, creatinuria, albuminuria, glucosuria).

SPSS version 22 and GraphPad Prism version 8 software for Windows will be used. Quantitative variables will be described in terms of median and interquartile range and qualitative variables in terms of absolute frequencies. To make comparisons before and after the training program, the Wilcoxon test or Student t test for related samples will be used, depending on the distribution of the variables. To investigate the presence of correlations between the variables of interest, the Spearman coefficient will be used. The sample size calculation was carried out considering the following parameters: a power of 95%, an alpha value of 0.05, a difference in pre- and post-

intervention means of 50 (100 vs 150) pg/ml, with a standard deviation for both groups of 50 pg/ml. With these data, the sample size is 16 participants, and considering a 20% drop-off, the final size is 20 participants. A p value < 0.05 will be considered statistically significant for all analyses.

Expected results: It is expected to observe that the variations in blood lactate induced by exercise will be associated with changes in plasma concentrations of FGF21, in order to postulate lactate as one of the factors that modulate the production of this factor, and that, therefore, it could play a relevant role in the normalization of the metabolic function associated with exercise.

BACKGROUND

Physical inactivity is defined as not reaching the minimum levels of spontaneous physical activity required to maintain a healthy life. In this sense, this parameter is defined by the World Health Organization as performing less than 150 minutes/week of moderate-intensity physical activity and/or less than 75 minutes/week of vigorous physical activity (1). Therefore, maintaining a physically inactive life leads to the development of a range of cardiorespiratory and metabolic diseases, among which arterial hypertension, dyslipidemia, obesity, insulin resistance and type 2 diabetes mellitus stand out (2, 3).

However, even when these alterations manifest and develop, it has been described that physical activity and exercise have the capacity to counteract and treat these dysfunctions (4). In this regard, it has been postulated that these effects are mediated by factors whose release from endocrine organs (e.g., liver, white adipose tissue, and skeletal muscle) are induced by physical effort derived from exercise (5), recently being called exerkines (6). In this context, one of the mediators that has attracted scientific attention is fibroblast growth factor 21 (FGF21), a protein mainly produced in the liver, adipose tissue, and muscle (7). This interest is related to the multiplicity of functions in which this factor participates, where the following stand out: the promotion of glucose uptake, lipid oxidation, increased energy expenditure, and anti-inflammatory effects; all of these functions favor the prevention or treatment of metabolic dysfunctions associated with obesity (8), so the manipulation of FGF21 has been the subject of research in the field of management of metabolic dysfunctions associated with physical inactivity and obesity. This protein (~20 kDa) exerts its function by binding to FGFR 1 or 2 receptors, in addition to the binding of a co-receptor known as β -klotho to form a 1:2 hetero-complex (7, 9). Since the presence of these receptors and co-receptor is found in different tissues, such as white adipose tissue, skeletal muscle, heart, pancreas and brown adipose tissue (8), it is hypothesized that FGF21 can exert its metabolic functions in all of them, so that its manipulation would have rather systemic effects (Figure 1).

In this regard, recent literature has shown that circulatory levels of FGF21 change after physical exercise. Thus, in the face of a session of exercise at moderate intensities of effort, circulatory levels of FGF21 tend to increase by 20% compared to baseline values in sedentary people with overweight or obesity (10, 11). However, other authors have not found significant variations, despite subjecting participants to exercise sessions with similar characteristics (12, 13). This highlights the fact that it is unknown, to date, whether there are intermediate stimuli between physical exercise and the increase in FGF21 from its endocrine origins.

On the other hand, lactate has traditionally been described as a waste metabolite resulting from anaerobic glycolysis that develops, among others, during processes of high intensity and short duration physical effort (14). However, recent studies show that lactate has multiple cell signaling functions which, in part, have implications in the regulation of the metabolism of different tissues such as inhibiting lipolysis in white adipose tissue, regulating redox balance in skeletal muscle and promoting gluconeogenesis in the liver and kidney (15). Thus, investigating potential associations between circulating lactate during exercise and metabolism in skeletal muscle, Hojman et al. observed in a mixed model (humans, mice and myocyte cell culture) that elevations in blood lactate were related to elevations of the well-known myokine interleukin (IL) 6, and that the release of IL6 from muscle cells was from vesicles that required the activity of matrix metalloproteinases, which in

turn were activated by lactate signaling (16). Studies such as this have opened the door to the study of the metabolic mediating function of lactate, especially during physical exercise.

Considering the above, lactate has recently been proposed as a potential mediator of FGF21 release. Thus, Jeanson et al. described rapid elevations of FGF21 from mouse adipocytes after treatment with increasing concentrations of lactate, where the authors hypothesized that these elevations of FGF21 could have both autocrine and endocrine characteristics (17). In addition, similar results were described by Villarroya et al. in myotubes, in which increasing concentrations of lactate correspondingly and autocrinely increased the concentrations of FGF21, both in terms of messenger RNA and protein (18). The authors detail that the lactate concentrations necessary to produce these effects are in the order of >3 mM, concentrations that can be physiologically found in the circulation during physical exercise, particularly at moderate to high intensities (19). In addition, it has been described that blood lactate is also related to markers of function of other organs of high metabolic relevance, such as the kidney and liver. Thus, in people with type 2 diabetes mellitus (DM2), serum lactate levels were independently and positively related to alanine aminotransferase (GPT) levels (20), so it would be interesting to observe whether high-intensity physical efforts, which generate significant elevations of lactate, influence these markers of liver damage. From a renal point of view, similar results were found in a similar sample of more than a thousand people with DM2 in which, even in the absence of renal dysfunction, positive relationships were observed between blood lactate and creatinine, urea nitrogen, as well as with the transaminase GPT (21). Therefore, it would be relevant to observe whether high-intensity physical efforts have an impact on these markers of renal function acutely (after a session) in order to manage safety parameters when implementing these intervention strategies in physically inactive people.

Taken together, these findings suggest that lactate would play a relevant role in the regulation of circulating concentrations of FGF21, as well as markers of tissue stress in the kidney and liver. However, the evidence in this regard is based mainly on findings in cell cultures or observational clinical studies, highlighting the absence of quasi-experimental or experimental clinical studies focused on solving this problem, in order to explore the potential relationships between transient elevations of circulating lactate during exercise with those of other metabolic mediators such as FGF21 and tissue function markers (e.g. liver and kidney) (Figure 2). Therefore, and taking advantage of the widely described elevations of lactate concentrations after high-intensity exercise and/or close to fatigue levels (14), the present study aims to investigate the influence of variations in lactate concentrations on circulating FGF21 after incremental physical exercise until fatigue, in a clinical context.

Working hypothesis

The expected increase in blood lactate following incremental exercise to fatigue will increase plasma levels of FGF21 in physically inactive adults.

General aim

To investigate the influence of exercise-influenced changes in blood lactate on plasma concentration of FGF21 in physically inactive individuals.

Specific aims

- To characterize the phenotype of the study sample.
- To compare blood lactate levels pre and post incremental exercise.
- To compare plasma FGF21 levels pre and post incremental exercise.
- To relate changes in blood lactate to changes in plasma FGF21 pre and post incremental exercise.

Secondary aims

- To compare blood levels of kidney function markers in blood (creatinine, urea nitrogen, urea acid and urea) and urine pre and post incremental exercise.
- To compare blood levels of transaminases (GPT and GOT) pre and post incremental exercise.
- To relate changes in blood lactate to changes in renal function markers and blood transaminases pre and post incremental exercise.

METHODOLOGY

Design: This is a quasi-experimental study comparing pre- and post-intervention. The research question is associated with investigating the influence of changes in blood lactate influenced by exercise on the plasma concentration of FGF21 in physically inactive people. This project has the approval of the Scientific Ethics Committee of the Valdivia Health Service (Ord. 222/2022) and has Biosafety certification by the Institutional Biosafety Committee of the Austral University of Chile (No. 36/23).

Sample: People over 18 years of age (and up to 30 years of age) enrolled in the Kinesiology program at the Austral University of Chile will be included. They must be physically inactive (perform less than 150 minutes/week of moderate physical activity and/or 75 minutes/week of vigorous physical activity) and without medical contraindications to perform physical activity. People who are taking medications that influence blood glucose or insulin levels and/or with anti-inflammatory effects will be excluded. The sample size calculation was performed considering the following parameters: a power of 95%, an alpha value of 0.05, a difference in pre- and post-intervention means of FGF21 of 50 pg/ml (100 vs 150 pg/ml), with a standard deviation for both groups of 50 pg/ml (according to the studies by Sabaratnam et al. and Slusher et al.: references 10 and 11 of point 3.1). With these data, the sample size is 16 participants, and considering a 20% drop-off, the final size is 20 participants, where recruitment will be by convenience and maintaining gender parity.

Variables: At the time of entering the study, the age in years and sex of the participants will be recorded. Anthropometric variables such as weight in kilograms and height in meters will be

recorded using a scale (InBody® 270) and a height rod (SECA) respectively. From these measurements, the body mass index (BMI) will be calculated in kilograms/meters². For the calculations of the waist-hip ratio (WHR) and waist-height ratio (WHR), the waist circumference will be measured in centimetres using the navel area as a reference point. The hip circumference will be measured as the largest circumference obtained at the trochanteric femoral level. The levels of total and segmental muscle and fat mass will be measured using the InBody® 270 bioimpedance meter. The level of spontaneous physical activity will be measured using the International Physical Activity Questionnaire (IPAQ) in its short version. To induce elevations in blood lactate, an incremental load test will be applied on a cycle ergometer or stationary bicycle, in which the pedalling load will be increased by 30W every 3 minutes, starting from an initial load of 30W until reaching the point of fatigue. Before starting the test, participants will remain seated for 10 minutes, during which time heart rate, subjective sense of exertion (SSE) with the modified Borg Scale, blood pressure, pulse oximetry and muscle (vastus lateralis of quadriceps) will be recorded at rest. In addition, a venous blood sample will be taken in a 2 ml tube with EDTA and another tube without anticoagulant for the subsequent plasma measurement of FGF21 with a specific ELISA kit for this (RayBio® catalog ELH-FGF21) and complementary biochemical tests (glycemia, insulinemia, total cholesterol, triglycerides, HDL, LDL, VLDL, non-HDL cholesterol, transaminases (GOT and GPT), creatinine, uric acid, urea and urea nitrogen). In addition, lactate measurement will be performed from a digital prick with a sterile lancet. For this, a specific reactive strip will be used, which will be measured with the AccuTrend Plus® device. In parallel, the participant will be asked to bring a urine sample from the same day on an empty stomach for biochemical analysis (proteinuria, creatinine clearance, albuminuria, glucosuria). Once these measurements have been taken at rest, the incremental stress test will begin. Thus, on a cycle ergometer each participant will begin the test with a pedalling cadence of 60-70 RPM at 30W load. Every 3 minutes this load will increase by 30W, always maintaining the same pedalling cadence. During the execution of the test, participants will always be supervised and guided by a professional kinesiologist. Heart rate, pulse and muscle oximetry, and SSE will be assessed minute by minute, while blood pressure will be measured every 3 minutes. At the end of the test, the test execution time, the distance travelled in meters, heart rate, blood pressure, SSE and final pulse and muscle oximetry will be recorded. The percentage of frequency reserve used during the test will be calculated with the Karvonen formula, which depends on the heart rates at rest and post-test. Fatigue at the end of the test will be understood as or the fulfillment of one or more of the following criteria: use of heart rate reserve $\geq 90\%$, subjective feeling of effort $\geq 18/20$ according to the original Borg scale, blood pressure $\geq 200/100$ mg of Hg, desire of the participant to finish the test (Figure 3).

Immediately after the test, a new venous blood sample will be taken in a 2 ml EDTA tube and in another tube without anticoagulant. In addition, the post-exercise blood lactate concentration will be measured by finger prick using a specific reagent strip and with the AccuTrend Plus® device. In addition, a post-exercise urine sample will be requested for biochemical analysis previously described. Subsequently, the participant's vital signs will be monitored for 10 minutes after the test to ensure proper recovery.

It is reiterated that, as an assessment of potential confounding/intermediate variables, the following biochemical parameters will be measured from blood samples taken pre- and post-exercise: Total cholesterol, triglycerides, HDL, LDL, VLDL, non-HDL cholesterol, insulin, glucose and transaminases

(GOT, GPT), creatinine, uric acid, urea and urea nitrogen. While, for urine samples, the levels of proteinuria, albuminuria, creatinine clearance, and glucosuria will be assessed.

Statistical analysis

Quantitative variables will be expressed as median and interquartile range, while qualitative variables will be described in terms of absolute frequencies. To calculate potential differences between pre- and post-stress test values, particularly lactate and FGF21, as well as transaminase levels and kidney function markers, the Wilcoxon test or Student t test for related samples will be used, depending on how the data distribution behaves (normal or nonparametric). In addition, associations between lactate and FGF21 concentrations, both pre- and post-exercise, will be explored using the Spearman correlation index and bivariate regression models. In addition, other potential associations of interest will be explored using the Spearman correlation index. For all analyses, a p value equal to or less than 0.05 will be considered statistically significant, using SPSS version 20 and GraphPad version 8 software.

References

1. OMS. Physical Inactivity 2022 [Available from: <https://www.who.int/data/gho/indicator-metadata-registry/imr-details/3416>.
3. Pedersen BK. The diseasesome of physical inactivity - and the role of myokines in muscle-fat cross talk. *The Journal of Physiology*. 2009;587(23):5559-68.

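### The baseline urine is a brought-in sample with no void required before the test, so the urine comparison cannot isolate the acute effect of exercise

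*Protocol*

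**What the plan says.** The Abstract says only that "urine samples will be taken both before and after exercise to measure renal function markers". The procedure is in the Methodology. For the baseline, under Variables: "In parallel, the participant will be asked to bring a urine sample from the same day on an empty stomach for biochemical analysis". After the test, "In addition, a post-exercise urine sample will be requested for biochemical analysis previously described". Neither sentence gives a clock time, an interval to the test or a volume, and nowhere is the participant told to empty the bladder before exercise.

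Blood and lactate are handled differently. They are sampled around a seated rest ("Before starting the test, participants will remain seated for 10 minutes"), and venous blood is drawn again immediately after the test. The brought urine is listed with these resting items, and then "Once these measurements have been taken at rest, the incremental stress test will begin".

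The urine pair serves the first secondary aim: "To compare blood levels of kidney function markers in blood (creatinine, urea nitrogen, urea acid and urea) and urine pre and post incremental exercise". The third secondary aim relates lactate change to change in renal markers. The Background gives the purpose as the acute effect of one session, with safety in mind. The Statistical analysis section applies a paired t or Wilcoxon test.

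**The concern.** A paired comparison measures the acute effect only if the two samples bracket the exposure. The blood pair does. The urine pair need not: the post-exercise void contains whatever has collected since the bladder was last emptied, and the plan does not say when that was. Pre-exercise urine in that void pulls the measured change towards zero. For a question asked partly for safety this is the unfavourable direction, because a diluted signal looks like no renal effect.

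The carried-over share depends on each participant's gap and test length, neither of which is fixed. For the third secondary aim this does more than add noise. If longer tests go with larger lactate changes, the share of exercise urine varies with lactate, and the association is distorted.

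A fasting sample and a later sample may also differ in concentration for reasons unrelated to exercise. Analysis cannot remove carry-over that was never measured, so this has to be settled in the collection procedure.

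**Working it through.** **The plan's own figures.** The Protocol gives none for urine. Its only calculation, 16 participants raised to 20, concerns FGF21. It reproduces with a two-sided paired t test if the SD of the difference is 50 pg/ml (n = 16, power 96.2%; 16/0.8 = 20), and this point does not affect it.

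**From the Protocol.** The test is described as follows: "the pedalling load will be increased by 30W every 3 minutes, starting from an initial load of 30W until reaching the point of fatigue". Duration is not stated.

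**Assumed, because the Protocol is silent.** Test length T = 20 min; urine flow 1 mL/min at rest and e = 0.5 to 1 mL/min in exercise; gap c = 10 to 180 min from last void to start of test; post-exercise void as exercise ends.

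**Formulas.** Exercise share of the post sample: f = eT / (eT + 1 × c). If urine formed in exercise has R times the resting concentration, the post sample shows 1 + f(R − 1). With R = 5:

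| Gap c | f, e = 0.5 | Apparent rise | f, e = 1 | Apparent rise |
|---|---|---|---|---|
| 10 min | 10/20 = 50% | 3.0-fold | 20/30 = 67% | 3.7-fold |
| 60 min | 10/70 = 14% | 1.6-fold | 20/80 = 25% | 2.0-fold |
| 120 min | 10/130 = 8% | 1.3-fold | 20/140 = 14% | 1.6-fold |
| 180 min | 10/190 = 5% | 1.2-fold | 20/200 = 10% | 1.4-fold |

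With a void just before the test, c = 0 and f = 100%.

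**Variation between participants.** At equal flow and a 60-minute gap, a 12-minute test gives 12/72 = 17% and a 24-minute test 24/84 = 29%. The same true 5-fold rise then appears as 1 + 4 × 12/72 = 1.7-fold or 1 + 4 × 24/84 = 2.1-fold.

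**Effect on the paired test.** Take a true standardised paired effect of 1.0, n = 20 and an unchanged SD of the difference. Power falls from 99% without mixing to 57% at a 50% share, 19% at 25% and 7% at 10%. If mixing also narrows the spread of changes, the loss is smaller.

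**Does a creatinine ratio cure it?** If creatinine is excreted at a constant rate, the exercise period's weight in the ratio is T/(T + c): 20/30 = 67%, 20/80 = 25% and 20/200 = 10% at gaps of 10, 60 and 180 minutes. The ratio removes differences in concentration but leaves the carry-over.

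**The case against.** Several objections limit the point.

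- A reader might infer that the comparison cannot show an acute effect at all. The text does not support that. Nothing bars a participant from voiding shortly before the test, so mixing is likely but not certain. With a short gap most of a large rise survives, and even the diluted rises above might be detected.
- A reader might also infer that the baseline is a concentrated overnight specimen collected at home, so that a true rise could be reversed. Being brought in and fasting does not establish where or when it was voided, how concentrated it was, or the participant's posture in between. An assumed 2:1 concentration ratio would turn unchanged excretion into a 50% fall, but that only restates the assumption. What stands is that the samples may differ in concentration, by an unknown amount.
- The magnitude rests wholly on assumptions. Only the venous draw is tied to the moment after the test, so a later urine void would contain more urine formed after the test began. If a 5-fold rise means excretion rate rather than concentration, halved flow makes it 10-fold in concentration, and the 180-minute case becomes 1 + 9 × 10/190 = 1.5-fold.
- The first and third secondary aims also use blood creatinine, urea, urea nitrogen and uric acid, as well as transaminases for the third. These are drawn at rest and after the test and are not affected.

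None of this supplies the missing interval or pre-test void.

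**Conclusion.** The point holds for the urine markers only. As written, the procedure lets pre-exercise urine enter the post-exercise sample by an uncontrolled amount, which biases the acute comparison towards no change. The urine part of the first and third secondary aims therefore cannot isolate the effect of the session, and a null urine result would not be evidence of renal safety.

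The loss runs from moderate at a 10-minute gap (5-fold seen as 3.0- to 3.7-fold) to severe at 60-180 minutes (1.2- to 2.0-fold). That range illustrates assumed gap, flow, test length and void time; it does not estimate what this study will see. The hypothesis, FGF21, lactate and the blood markers stand. The procedure should be corrected, but the main aim does not depend on it.

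**What to change.** Make three changes to the Methodology:

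1. Replace the brought sample with a complete void at the site just before the test, and use that void as the pre-exercise sample.
2. Collect the post-exercise urine at one fixed time after the test, the same for everyone and late enough to give an adequate volume.
3. Compare albumin and protein as ratios to urinary creatinine. The Abstract already lists creatinuria; the Methodology lists creatinine clearance instead, so urinary creatinine should be named there too. The ratio handles concentration, and only the pre-test void handles carry-over.

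The number of urine samples is unchanged, and no assay is added beyond those the Abstract already lists. The costs are practical. Some participants may need a short wait to void before the test. After a complete void, the flows assumed above leave only 20 × 0.5 = 10 mL to 20 × 1 = 20 mL at the end of a 20-minute test, so the fixed collection time will have to include some recovery urine, and the report should say so. These changes alone do not settle creatinine clearance, which also needs the collection interval and urine volume recorded.

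### Urine protein, albumin and glucose are compared before and after exercise with no correction for urine concentration, so a dilution change can mimic or hide a change in kidney markers

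*Protocol*

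**What the plan says.** Before the test, according to Methodology (Variables), "the participant will be asked to bring a urine sample from the same day on an empty stomach for biochemical analysis". After it, "a post-exercise urine sample will be requested for biochemical analysis previously described". Neither sentence gives a collection interval or a urine volume.

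The measured quantities are named twice, and differently. The Abstract says "urine samples will be taken both before and after exercise to measure renal function markers (proteinuria, creatinuria, albuminuria, glucosuria". Methodology, just before Statistical analysis, says "While, for urine samples, the levels of proteinuria, albuminuria, creatinine clearance, and glucosuria will be assessed". Creatinuria in the first list has become creatinine clearance in the second.

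Two secondary aims use these data: "To compare blood levels of kidney function markers in blood (creatinine, urea nitrogen, urea acid and urea) and urine pre and post incremental exercise" and "To relate changes in blood lactate to changes in renal function markers and blood transaminases pre and post incremental exercise". For the pre/post comparison the Statistical analysis section says: "as well as transaminase levels and kidney function markers, the Wilcoxon test or Student t test for related samples will be used", with the choice between the two depending on the distribution. Other associations of interest go to Spearman correlation.

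No section mentions a ratio to creatinine, an excretion rate or any other allowance for urine concentration.

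**The concern.** The level of a substance in an untimed urine sample depends on how much is excreted and on how much water it is dissolved in. Only the first concerns the kidney markers the aims ask about. The two samples are taken under different conditions, one fasting and one after incremental exercise to fatigue, and the document says nothing about fluid intake. The study has a single group, so no control arm can absorb a shift in urine concentration shared by the participants.

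The Background says the acute renal markers are of interest for the safety of high-intensity effort in inactive people. More concentrated urine could therefore give a false signal, and more dilute urine false reassurance. The aim relating renal changes to lactate changes uses the same quantities. Listing creatinuria as a kidney marker in its own right adds to the problem, because in an untimed sample it also moves with urine concentration.

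**Working it through.** **The plan's own figure.** The only computed figure is the sample size for FGF21 ("a power of 95%, an alpha value of 0.05, a difference in pre- and post-intervention means of FGF21 of 50 pg/ml", SD 50 at each time point). With an SD of the difference of 50, which assumes a pre/post correlation of 0.5 that is not stated, a two-sided paired t test needs n = 16 (power 0.962), and 16 / 0.8 = 20. The stated 16 and 20 reproduce. They do not bear on the urine point except to set n below.

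**Step 1: what a level measures.** Concentration = excretion rate / urine flow, so

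post/pre level = (excretion ratio) / (flow ratio).

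The document gives no flow values; those below are assumptions.

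| Flow ratio | True excretion ratio | Level reads |
|---|---|---|
| 0.5 | 1.0 | 1 / 0.5 = 2.0 |
| 0.67 | 1.0 | 1 / 0.67 = 1.49 |
| 1.5 | 1.0 | 1 / 1.5 = 0.67 |
| 2 | 1.0 | 1 / 2 = 0.5 |
| 1.5 | 1.5 | 1.5 / 1.5 = 1.0 |
| 2 | 2.0 | 2 / 2 = 1.0 |

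**Step 2: what the paired test does with it.** Simulation: 20,000 trials per setting, paired t test on log level, two-sided 0.05, n = 20. The SD of the log change is assumed to be 0.5 (range in brackets: 0.7 to 0.3).

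- No change in excretion, no mean change in flow: significant in about 5% of trials.
- No change in excretion, mean flow down 20%: about 48% (26% to 89%).
- No change in excretion, mean flow down 33%: about 92% (68% to 100%).
- True 1.5-fold rise in excretion, flow unchanged: detected as a rise in about 93% (70% to 100%).
- The same rise with flow up 1.25-fold: about 35% (20% to 73%).
- The same rise with flow up about 1.5-fold: about 3%.

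With n = 16 and SD 0.5, the second and third lines become about 39% and 85%.

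The first line matters for the reading. Changes in concentration that differ between participants but average to nothing leave the error rate at 5% and only add noise. The bias needs a shift in the mean.

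**Step 3: the ratio to creatinine.** Analyte and creatinine share the same flow, which cancels:

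post/pre ratio = (analyte excretion ratio) / (creatinine excretion ratio).

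With steady creatinine excretion every row of the table returns its true excretion ratio. If creatinine excretion rises 20%, a true 1.0 reads 1 / 1.2 = 0.83; if it falls 20%, 1 / 0.8 = 1.25.

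**Step 4: the lactate correlation.** A concentration shift unrelated to lactate change only adds noise to this correlation. It creates a false association only if participants with larger lactate rises also have systematically more (or less) concentrated urine after exercise.

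**The case against.** A fair defence has four parts.

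- The document never uses the term spot sample and gives no units. Its word for the urine results also covers creatinine clearance, a derived quantity, so it need not mean raw concentration. Protein, albumin and creatinine are exactly what ratio reporting would need. This stands as a limit: raw untimed concentration is inferred from the absence of timing, volume and any stated ratio.
- Expression of laboratory values is often left to a SAP or laboratory procedure. This carries less weight here. The document is titled as both protocol and SAP, names the quantity and the test, and lists creatinuria as a marker rather than a denominator.
- The Statistical analysis section names no urine analyte, and the repeated list of blood and urine measurements is introduced as covering possible confounders or intermediates. The link to urine nevertheless follows from the first secondary aim.
- The ratio has its own weakness, since creatinine excretion may change with maximal exercise. This stands and belongs in the limitations. Compulsory log ratios would also fail for zero or below-detection values and would displace the planned choice between Wilcoxon and t test without need.

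A reader might infer that the urine results will be biased in a known direction because most participants' urine shifts the same way. The document does not support that: it gives no flow, hydration or fluid-intake information. A reader might also infer that test duration will produce a false lactate-kidney association. That is conjecture, as nothing in the document links duration to urine concentration.

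**Conclusion.** The point holds as a conditional one. Untimed pre/post urine levels without correction cannot separate a change in excretion from a change in urine concentration. If mean concentration differs between the two samples, the paired comparison can be wrong in either direction, and a larger sample does not cure it. For flow ratios assumed between 0.5 and 2, unchanged excretion reads anywhere from 2.0 down to 0.5. The residual error of the creatinine ratio, for an assumed 20% shift in creatinine excretion either way, is 0.83 to 1.25.

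The size and direction in this trial are unknown, and every flow and SD value above is an assumption. Only the urine part of the secondary renal aims is affected. Lactate, FGF21, the blood renal markers and the transaminases are untouched. It should be corrected, but it does not threaten the main comparison.

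**What to change.** In the Secondary aims, Variables and Statistical analysis text:

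- Define the urine outcomes as albumin/creatinine and protein/creatinine, and glucose/creatinine where glucose is quantifiable, each from a single sample.
- Test them with the paired Wilcoxon or t test already planned. A log scale is optional; state a rule for values below detection.
- Use the changes in these ratios in the correlations with lactate change.
- Report urine creatinine as the denominator, not as a separately tested kidney marker.
- Reconcile creatinuria (Abstract) with creatinine clearance (Methodology). Clearance needs a timed urine volume, which the described collection does not provide.
- State as a limitation that the ratio assumes fairly stable creatinine excretion across the test, with the 20% example above.

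The cost is wording and one division per sample. Urine creatinine is already on the Abstract's list and is needed for the clearance that Methodology names.
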